#### **7.2.6. Quantitative Muscle Strength**

In our disease progression model specified in 3.3.1, the rate of progression for each muscle was determined. Given baseline data for each subject, we can then predict the percentage of strength for each primary muscle group for each subject at their follow-up visits. To investigate if ManNAc affects disease progression we will provide descriptive statistics of the predicted percentage of strength for each primary muscle group versus the measured percentage of strength at every visit. We will also more formally explore the possibility of the ManNAc causing a change in the rate of decay of the muscles over a 24-month period by introducing a proportional treatment effect on the rate of decline ( $\gamma$ ) into the disease progression at the time of treatment. If  $\gamma$  is equal to 1 there is no effect of the treatment on the disease progression model and the treatment effect model is the same as the normal disease progression model. If  $\gamma$  is less than one the treatment slows the rate of decay of the muscle group and if  $\gamma$  is equal to zero the treatment has stopped the decay of the muscle group altogether. If  $\gamma$  is greater than one the treatment increases the rate of decay of the muscle group. Under this treatment effect model we will report the posterior mean, and 95% credible interval for  $\gamma$  as well as the posterior probability that the treatment slows the rate of decay of the muscle groups ( $\gamma$  is less than one).

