#### 3.3.1. Progression Model GNE Myopathy

A disease progression model was developed utilizing the natural history data of 32 GNE myopathy subjects, to determine the average rate of decay of selected muscle groups. The primary endpoint used was Quantitative Muscle Assessment (QMA). For each available QMA measurement a corresponding predicted muscle score is calculated based on the subject’s age, gender and BMI and the proportion of QMA muscle score relative to the predicted score, referred to as proportion of strength, was used. The primary endpoint of the disease progression model is the proportion of strength across the primary muscle groups: 1) Ankle dorsiflexion (anterior tibialis muscle), 2) Knee flexion (hamstrings), 3) Grip, 4) Hip extension, and 5) Knee extension (quadriceps), and 6) Shoulder abduction (deltoid).

The stage of disease varies among subjects, so the model accommodates subjects at varying stages of the disease by estimating a disease age for each subject based on their decline in the proportion of muscle strength (QMA muscle score relative to predicted muscle score) within 5 primary muscle groups. Disease age zero is defined when knee flexion is .50 of the maximum muscle strength. Given this estimate of disease age we are able to align the subjects and estimate an expected decay of each of the 5 primary muscle groups relative to one another and as a function of disease age ([Figure 2](#)). This allows us to understand the rate of progression of muscles groups relative to one another and to make subject-specific predictions of their decline.

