### 3.8.5. Muscle Strength

One of the secondary objectives of the Phase 2 study is to evaluate suitable endpoints for future trials. Because there is muscle atrophy and replacement of muscle by fibro-fatty tissue as part of the disease process, reversal of disease progression is unlikely. Rather, a slowing in the rate of progression is the expected treatment effect.

As part of this, muscle strength measured by QMA has been collected at every visit. All 12 patients participating in the open-label study were prior participants of the Natural History Study, and therefore, their ‘natural history’ rate of progression (prior to ManNAc administration) has been determined.

To evaluate the performance of the disease progression model when incorporating treatment effect, data from the Phase 2 was tested in the model, to compare the rate of progression after initiation of ManNAc to the rate of progression before intervention. At 182 days (6 months), a preliminary analysis shows a posterior mean of  $\gamma=0.49$  (95% CI: .02-1.35). At 182 days (12 months), another preliminary analysis shows the current mean estimate for  $\gamma$  is approximately 0.61 (95% CI (0.09, 1.27), and the posterior probability that  $\gamma$  is less than 1 is 0.89. The most recent analysis at 548 days (18 months), shows a  $\gamma=0.55$  with a posterior probability that  $\gamma$  is less than 1 is 0.966. This means, the model estimates a 45% slowing in the rate of decline on subjects receiving ManNAc with a probability that there has been slowing in progression of 96.6%.

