#### **4.11. Randomization and Blinding**

There will be no blinding or randomization.

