**Figure 7. MRS of GNE Myopathy Muscle**

### 5.2.1.3. Quantitative Muscle Strength Assessment (QMA)

Muscle strength will be evaluated at baseline and at every follow-up visit utilizing the Quantitative Muscle Strength Assessment (QMA) which measures maximal voluntary isometric contraction (MVIC) in kilograms (kg) using a fixed frame dynamometer, a strain gauge tensiometer, and a computer-aided acquisition system (Aeverl Medical, Gainesville GA, USA) to measure maximal strength in 13 muscles groups. The muscle strength in kg is compared to predicted strength for age, gender, height and weight to generate a proportion of predicted strength value.

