#### 7.1.1. General Reporting Conventions

Standard descriptive statistics will include the number (n), mean and standard deviation (SD), median, minimum, and maximum values for continuous variables. For categorical variables, the frequency of subjects will be provided along with the percentage based on the number of subjects with available data. Unless otherwise indicated, summaries will be based on observed data (i.e., no missing data will be imputed).

Any statistical testing and/or provided confidence intervals (CI) are provided as an aid in interpreting study results and are not intended as claims. Results from this study may be used in designing future studies.

Summaries will be provided by treatment group for the individual ManNAc treatment groups (6,000 mg and 12,000 mg), a combined ManNAc group and the combined control subjects from all two cohorts.

Analyses will be generated using SAS® version 9.2 or higher. Analysis on QMA will be performed using R®.

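### Section 7.2.6 describes no term for a level change after first dose, so a lasting effort or expectation gain in open-label strength testing would be partly counted as slower decline

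*Combined protocol and SAP*

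**What the plan says.** Section 7.2.6 takes the natural-history progression model, built "utilizing the natural history data of 32 GNE myopathy subjects" (Section 3.3.1), and extends it by "introducing a proportional treatment effect on the rate of decline" from the start of treatment. It will report the posterior mean of gamma, a 95% credible interval and the posterior probability that gamma is below 1. It also plans a descriptive comparison of predicted and measured strength at each visit. No step, visit-number or learning term is described.

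The endpoint is QMA, which "measures maximal voluntary isometric contraction (MVIC) in kilograms (kg" (Section 5.2.1.3). Section 4.11 states: "There will be no blinding or randomization". Section 3.8.5 describes the preliminary use of the model as being "to compare the rate of progression after initiation of ManNAc to the rate of progression before intervention", and notes that "All 12 patients participating in the open-label study were prior participants of the Natural History Study".

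Three preliminary results appear in Section 3.8.5:
- 6 months: gamma 0.49 (interval 0.02 to 1.35).
- 12 months: gamma 0.61 (0.09 to 1.27), with P(gamma<1) = 0.89. The text labels this analysis 182 days, which does not affect the check below.
- 18 months: gamma 0.55, with P(gamma<1) = 0.966.

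Section 7.1.1 says that tests and intervals are interpretive aids and not claims. It also promises summaries for "the combined control subjects from all two cohorts", a group that this design does not contain.

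**The concern.** In a before-and-after comparison with one treatment-period parameter, anything lasting that begins after first dose has to be absorbed somewhere. If subjects try harder, or testers encourage them more, once open-label drug has started, measured strength rises by a roughly constant amount. The model has no place for a constant amount, so part of it goes into the rate.

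The natural-history model controls for disease stage and ordinary decline. It does not control for other things that start with the drug.

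Gamma is used despite the caveat in Section 7.1.1. Section 3.8.5 concludes that "the model estimates a 45% slowing in the rate of decline on subjects receiving ManNAc". Section 3.3.1.1 says the extension will inform the effect size for the pivotal trial. Reading that section's simulations by percentage slowing, trial success is about 98.8% when decline slows by at least 50%, but 75.5% when it slows by 25%. An overstated gamma would make the next trial look safer than it is.

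**Working it through.** **Inputs.** QMA visits follow Appendix C: Days 85, 180, 365, 548, 730 and 912. Dividing by 365.25 gives t = 0.233, 0.493, 0.999, 1.500, 1.999 and 2.497 years. The gammas, intervals and probabilities come from Section 3.8.5. The untreated decline r and the gain s are not in the documents, so the gain is expressed as s/r, in time-equivalents of untreated decline.

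**Reproducing the plan's figure.** At 12 months, SD = (1.27 − 0.09)/(2 × 1.96) = 0.301. Then P(gamma<1) = Φ((1 − 0.61)/0.301) = 0.90, against 0.89 stated, so a normal approximation serves. At 18 months the implied SD is (1 − 0.55)/1.825 = 0.247, where 1.825 is the normal quantile for 0.966.

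**Size of the shift, baseline fixed.** Take y(t) = baseline − gamma × r × t. If true gamma is 1 and a persistent gain s follows first dose, least squares gives

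fitted gamma = 1 − (s/r) × Σt/Σt².

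| Analysis | Σt | Σt² | Factor Σt/Σt² |
|---|---|---|---|
| 6 months | 0.726 | 0.297 | 2.44 |
| 12 months | 1.725 | 1.296 | 1.33 |
| 18 months | 3.225 | 3.547 | 0.91 |
| 24 months | 5.224 | 7.541 | 0.69 |

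For an inactive drug to give 0.55 at 18 months, s/r = 0.45/0.909 = 0.495 years, or 5.9 months of decline. For assumed r of 2, 3, 5 or 10 points of predicted strength per year, that is 1.0, 1.5, 2.5 or 4.9 points.

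**Baseline not fixed.** Section 3.3.1 estimates a disease age for each subject. If subject level is re-estimated jointly from one to four pre-dose visits (yearly spacing assumed, pre-dose slope known), the 18-month factor falls to between 0.44 and 0.72. The gain needed is then 0.45/0.440 = 1.02 years (12.3 months) down to 0.45/0.718 = 0.627 years (7.5 months).

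**Effect on P(gamma<1).** With SD 0.247, a fixed baseline and an inactive drug, the chance of reaching 0.966 or more at 18 months is:
- no gain: 3.4%
- gain worth 3 months: 1 − Φ(1.825 − 0.227/0.247) = 18%
- gain worth 6 months: 51%

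A simulation with 12 subjects gave 3%, 19% and 52%.

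**Do the reported values look like a step?**

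| | 6 months | 12 months | 18 months |
|---|---|---|---|
| Reported | 0.49 | 0.61 | 0.55 |
| Inactive drug, gain worth 5.9 months | −0.21 | 0.34 | 0.55 |
| True gamma 0.80, gain worth 3.3 months | 0.13 | 0.43 | 0.55 |

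The third row is 0.80 − 0.275 × factor. Its 6- and 12-month values lie inside the reported intervals. The pure-step value of −0.21 lies below the 6-month interval.

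**With a level-shift term.** In the simulation, mean gamma returns to 0.99 to 1.00 for gains worth 0, 3 or 6 months. With baseline fixed, the SD inflation at 18 months is √(Σt²/Σ(t − mean)²) = √(3.547/0.946) = 1.94, so the SD goes from 0.247 to 0.477. If the mean stayed at 0.55, P(gamma<1) would be Φ(0.45/0.477) = 0.83. Under joint re-estimation the inflation is 1.24 to 1.54.

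**The case against.** Most of the case on the other side stands as a limit on size.

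- **Practice.** All 12 subjects had been in the Natural History Study and had a QMA at trial baseline. A gain already present at baseline would be largely absorbed there. Practice is therefore a minor route. Effort and expectation after dosing are the live ones.
- **Fixed baseline.** This is the least favourable version of the model. Code and priors are not in the documents, so the true sensitivity is unknown, and no term means none described.
- **Permanence.** A gain that fades does less. One worth 6 months of decline with an assumed half-life of 12 months gives 0.78 at 18 months; with 6 months it gives 0.88.
- **Existing safeguards.** Predicted and measured strength are shown at every visit, and Section 7.4 plans analyses at 6, 12, 18, 24 and 30 months, so a step might be seen. But the comparison is descriptive, and nothing links a visible step to how gamma is reported.
- **Exploratory status.** Section 7.1.1 disclaims claims. That lowers the stakes for this study, but not for the pivotal design that gamma is meant to inform.

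A reader might infer that untreated Natural History participants, given a pretend start date, would settle the matter. They would not. They never begin open-label drug, so they cannot show its effect on effort. Gamma near 1 is also close to guaranteed in the data that built the curve.

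**Conclusion.** The concern holds as a gap in the analysis. Nothing in Section 7.2.6 separates a lasting level gain after first dose from a slower rate, and gamma is already being read as a rate effect. With a fixed baseline and a linear model, each month of decline-equivalent gain lowers the 18-month gamma by about 0.076 (0.909/12). Joint re-estimation of level or a fading gain makes this smaller but does not remove it. The bias also falls with follow-up: the gain that gives 0.55 at 18 months gives 0.66 at 24 months (1 − 0.495 × 0.693).

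A reader might go further and infer that the reported 45% slowing is an artefact. The documents do not support that. They give no evidence that a gain occurred and state neither its size nor the average decline. The sequence 0.49, 0.61, 0.55 also argues against a pure step. What remains possible is a partial gain: a true slowing of 20% could appear as 45%, as the third row of the comparison table shows.

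**What to change.** Keep the main gamma analysis unchanged. Add to Section 7.2.6 one sensitivity fit with a common level-shift parameter starting after first dose, its scale and prior stated in advance. Report gamma, its 95% credible interval and P(gamma<1) with and without the shift. Do not carry gamma into the pivotal design as a rate effect without showing both.

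The cost is SAP wording and one extra model run on data that the trial already collects. The downside is precision: gamma's SD in that fit is about 1.2 to 1.9 times larger. With 12 subjects at most, and eight remaining on 6 g twice daily at the review in Section 3.8.2.2, the fit may be unable to separate a step from a slope. That should be reported as such.

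A pseudo-start run in Natural History participants who never took ManNAc is optional. It needs data held out from model building, and it tests only model fit and repeat-testing drift. If slowing were claimed relative to it, the comparison would carry the error of both estimates.

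In Section 7.1.1, delete the reference to combined control subjects. Natural History participants cannot fill that role, because those summaries also cover adverse events and PK on drug.

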#### **7.2.7. Other Rehabilitation Medicine Evaluations**

Changes in clinical measurements will be analyzed as a change from baseline to last visit using a paired t-test or Wilcoxon rank sum test based on parametric quality of the data.

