#### **3.8.2.2. 15-HG-0068 Open-Label Phase 2 Study (ClinicalTrials.gov Identifier: NCT02346461)**

There have only been no Serious Adverse Events observed as part of this Open-Label Phase 2 Study. The SRC review included safety through 24 months on all subjects. The reviewed safety information included adverse events (AEs), ECGs, vital signs, physical assessments and clinical laboratory data. Eight subjects remain on 6 grams twice daily. Four subjects have withdrawn consent, two of which discontinued due to gastrointestinal tolerability, another planning on getting pregnant and another was withdrawn due to noncompliance. AEs for the cohort from the latest SRC review are in [Appendix G](#). Due to 8 out of 12 subjects participating in this trial, demonstrated gastrointestinal tolerability issues or AEs related to ManNAc and 16% had tolerability issues significant enough to discontinue their participation, we have attempted to better understand the etiology of the decreased tolerability. The clinical manifestations together with PK evaluations, strongly suggest that unabsorbed ManNAc in the gastrointestinal tract is the likely cause. As discussed below in [Section 3.9.1](#), we believe absorption of ManNAc can be increased by 20% by giving the same daily dose of ManNAc (12 grams) divided three times (4 grams TID) instead of twice daily (6 grams BID).

One subject in the study had Grade 3 hypertriglyceridemia which was determined to be probably related to ManNAc. As higher triglycerides were also seen in toxicology studies (see [Table 10](#)), hypertriglyceridemia is a risk associated with ManNAc.

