### 5.2.1.4. Other Rehabilitation Medicine Assessments

Other assessments may be performed at baseline and follow-up visits and will include muscle strength using the 10-point manual muscle testing (MMT-28) scale, Adult Myopathy Assessment Tool (AMAT), 6-min walk test (may be replaced by 10-meter walk test), timed up-and-go test, forward/functional reach test. The Jebsen Standardized Hand Function test will be done at baseline, 365 days (12 months) and 730 days (24 months).

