### **7.3. Determination of Sample Size**

Eligible subjects will be enrolled into one of 2 cohorts of 6 subjects each, to receive ManNAc at doses of 3,000 mg BID (n=6) or 6,000 mg BID (n=6). Given the rarity of disease and the intent of this study—determine pharmacokinetics, safety and efficacy using blood based and tissue biomarkers, 12 subjects should be suitable.

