
dependence, antisocial personality disorder, panic disorder, or behavioral problems, which interfere with effective communication.
 
 
3. Subject has hepatic laboratory parameters (AST, ALT, GGTP) or renal laboratory parameters (creatinine, BUN) greater than 3 times the upper limit of normal.
 
4. Subject has known adverse reactions to anesthetic or sedatives utilized for muscle biopsy.
 
5. Subject is anemic (defined as Hematocrit <30%) or has platelets <100,000 or white blood cell count less than 3,000.
 
6. Subject shows evidence of clinically significant cardiovascular, pulmonary, hepatic, renal, hematological, metabolic, or gastrointestinal disease, or has a condition that requires immediate surgical intervention.
 
7. Subject is pregnant or breastfeeding at any time during the study.
 
8. Subject has received treatment with another investigational drug, investigational device, or approved therapy for investigational use less than 90 days prior to the first protocol visit.
 
9. Subject has hypersensitivity to ManNAc/ManNAc or in the judgment of the investigator, has a condition that places the subject at increased risk for adverse effects.
 
10. The presence of persistent diarrhea or malabsorption that could interfere with the subject's ability to absorb drugs or to tolerate ManNAc therapy.
 

Investigational product, dosage, and mode of administration:  ManNAc (ManNAc) administered orally at either 3,000, or 6,000 mg twice daily (total daily dose of 6,000 or 12,000 mg, respectively).

Duration of treatment:  Study drug will be administered for 912 days.

Reference therapy, dosage, and mode of administration:  None

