## APPENDIX B. STUDY DESIGN

**APPENDIX C. SCHEDULE OF EVENTS**

Event	Baseline	PK Phase			Safety/Efficacy Phase						PK	Safety/ Efficacy					Phone Follow-up
	Day -30 to 0	Day 1	Day 2-6	Day 7	Day 8-9	Day 10 (±3)	Day 28 (±7)	Day 45 (±7)	Day 63 (±7)	Day 85 (±5)	Day 85-90 (±5)	Day 180 (±14)	Day 365 (±14)	Day 450, 638, 820 (±30)	Day 548, 912 (-30)	Day 730 (-30)	Day 120, 240, 300, 400, 638, 820 (±30)
Admission	X							X		X		X	X		X	X	
Informed consent	X																
Eligibility	X	X						X		X		X	X		X	X	
Medical history	X							X		X		X	X		X	X	
Physical exam 	X	X	X	X	X	X		X		X	X	X	X		X	X	
Vital signs 	X	X	X	X	X	X		X		X	X	X	X		X	X	
Safety Labs 	X		X		X	X		X		X	X	X	X	X 	X	X	
Pregnancy test 	X							X		X		X	X		X	X	
12-lead ECG	X			X						X			X			X	
Muscle MRI/MRS	X									X			X				X
QMA 	X									X		X	X		X	X	
Rehab Measures 	X									X		X	X		X	X	
Muscle Biopsy 	X									X							
Activity Monitor	X	X	X	X	X	X	X	X	X	X	X	X	X		X	X	X
Study drug administration		X	X	X	X	X	X	X	X	X	X	X	X		X	X	X
Blood for PK 		X	X	X				X		X	X	X	X		X	X	
Blood for PD 	X	X	X	X	X	X		X		X	X	X	X		X	X	
Research samples	X		X	X		X		X		X	X	X	X			X	
Adverse events		X	X	X	X	X	X	X	X	X	X	X	X		X	X	X
PRO 	X							X		X		X	X		X	X	
Medications	X	X	X	X	X	X	X	X	X	X	X	X	X		X	X	X
Discharge						X		X			X	X	X		X	X	
Phone call							X		X								X

 The initial physical exam may be conducted at any time between Screening and up to and including Baseline.

 Collect vital signs: temperature, respiration, blood pressure and heart rate at Baseline, pre-dose and at post-dose per unit's nursing schedule. Weight must be obtained at baseline to verify eligibility (required weight > 50 kg)

 Blood for clinical laboratory tests and urine for urinalysis. See 5.2.2 for a list of clinical laboratory tests.

 Pregnancy test is required in female subjects with childbearing potential within 7 days prior to starting administration of study drug

 Quantitative Muscle Strength at Baseline and follow up visits

 Other Rehab measures include MMT-28, AMAT, 6 Min walk (or 10 meter run), timed up-go test, forward/ functional reach test will be performed at baseline and every follow-up visit. Jebsen hand test to be performed only at baseline, 12, and 24 months.

 Muscle biopsy at Baseline and at 3 months

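### Section 7.2.7 measures functional change to an undefined 'last visit', which can pool unequal follow-up in a progressive disease, and it has no rule for subjects who change walk test

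*Combined protocol and SAP*

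**What the plan says.** Section 7.2.7 is the whole analysis plan for the functional tests other than QMA: "Changes in clinical measurements will be analyzed as a change from baseline to last visit using a paired t-test", with a Wilcoxon test as the alternative. It does not define the last visit, name a day, or say how early leavers are handled. Section 7.1.1 adds that "summaries will be based on observed data (i.e., no missing data will be imputed" unless otherwise indicated.

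The synopsis in Appendix A sets the length of treatment: "Study drug will be administered for 912 days". Appendix C marks the rehabilitation measures at baseline and then at Days 85, 180, 365, 548, 730 and 912. The Jebsen hand test is the exception, scheduled only at baseline, 12 and 24 months (section 5.2.1.4; Appendix C, footnote 6).

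Section 3.8.2.2 reports "Four subjects have withdrawn consent, two of which discontinued due to gastrointestinal tolerability". The other two were a planned pregnancy and noncompliance, and eight subjects remain on treatment. Section 5.9 requires only safety evaluations from those who leave, and says that they will be replaced.

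Section 5.2.1.4 lists the "6-min walk test (may be replaced by 10-meter walk test"), whereas footnote 6 of Appendix C has "6 Min walk (or 10 meter run"). Neither place says when the substitute is used, or how a subject with different tests at two visits is analysed.

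**The concern.** Section 3.1 describes a disease that keeps progressing, and section 3.8.5 expects treatment to slow the decline, not reverse it. The change in a functional score therefore depends on how long the subject was followed. If each subject's last attended visit goes into one paired comparison, a subject last tested at 3 months counts the same as one tested at 30 months, and the average decline comes out too small for a 30-month result. The study has no concurrent control group that would reveal this, and a smaller decline points the same way as the hoped-for effect.

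A secondary objective is to find clinical endpoints for later trials, and section 7.1.1 says that results may be used to design future studies. An understated rate of decline, or a comparison of endpoints measured over different intervals, would carry into those designs.

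The walk test raises a related problem. A distance covered in six minutes and a result on a 10-metre course cannot be subtracted, so a subject who changes test has no usable pair.

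**Working it through.** **Which visit is meant.** Three features favour each subject's own last attended visit.
- Jebsen has no 30-month assessment, so it could not be analysed if the last visit were Day 912.
- The neighbouring sections give a time when they intend one: 7.2.5 uses 90 days, and 7.2.6 uses every visit and a 24-month period.
- Section 7.4 plans interim analyses from Day 182, when Day 912 data do not yet exist.

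This is the better reading, but the text does not settle it. Both readings are worked below.

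**Inputs.** N = 12 (section 7.3, "12 subjects should be suitable"; no power calculation is given, so there is no figure to reproduce). Planned follow-up is 912 days. Four subjects have left and eight remain (section 3.8.2.2). Assumptions: the eight reach Day 912, decline is linear, and replacements are ignored. L is the day of a leaver's last functional test, which the documents do not give. r is the leavers' rate of decline relative to the completers'.

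**Reading A: last attended visit, equal rates (r = 1).**
Reported/true 30-month decline = (8 × 912 + 4 × L) / (12 × 912) = (7,296 + 4L) / 10,944.

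| All four leavers last tested | Ratio | Understatement |
|---|---|---|
| Day 85 | 7,636 / 10,944 = 0.70 | 30% |
| Day 180 | 8,016 / 10,944 = 0.73 | 27% |
| Day 365 | 8,756 / 10,944 = 0.80 | 20% |
| Day 548 | 9,488 / 10,944 = 0.87 | 13% |
| Day 730 | 10,216 / 10,944 = 0.93 | 7% |

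If the four were last tested on Days 85, 180, 365 and 548 in turn, the ratio is (7,296 + 1,178) / 10,944 = 0.77.

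With unequal rates the ratio is (8 + 4r × L/912) / (8 + 4r). This is below 1 for any positive r when L is below 912. On this reading the direction does not depend on why subjects left; only the size does.

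**Reading B: Day 912, observed subjects only.** The leavers drop out under section 7.1.1, and the ratio is 12 / (8 + 4r).
- r = 0.5: 12/10 = 1.20 (decline overstated)
- r = 1: 12/12 = 1.00 (no bias)
- r = 1.5: 12/14 = 0.86
- r = 2: 12/16 = 0.75

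The recorded reasons for leaving do not show whether r is above or below 1.

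**Jebsen.** A completer's change covers 730 days against 912 for the other tests: 730/912 = 0.80, an interval 20% shorter. This needs no assumption about dropout.

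**Walk test.** Suppose k of n subjects change test, lose their 6-minute-walk pair, and decline s times as fast as the rest. Reported/true decline is n / ((n − k) + k × s). For k = 2 and n = 12:
- s = 1: 12/12 = 1.00
- s = 2: 12/14 = 0.86
- s = 3: 12/16 = 0.75

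Both k and s are assumptions; the documents give neither.

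**The case against.** The strongest reply is that the last visit could simply be the final scheduled visit. The unequal-interval mechanism then disappears, and no bias follows unless leavers decline at a different rate. That cannot be excluded, so the direction is stated only for the last-attended reading. The plan would still have to name the day and say how leavers and Jebsen are treated.

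A second reply concerns the size. Section 3.8.2.2 says that the safety review ran through 24 months on all subjects, which fits poorly with four departures at 3 months and leans towards the smaller end. The sentence is ambiguous, so the range stays, but 30% is an extreme and not an expectation.

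Third, the consequence is limited. Section 7.2.7 tests change against zero, so a smaller decline makes worsening harder to demonstrate; it does not produce a significant benefit. The formal analysis of slowing is the QMA progression model in section 7.2.6, which uses rates and is untouched. Section 7.1.1 also says that tests are interpretive aids. All of this stands, and it confines the point to the secondary functional measures.

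A reader might also infer that the 6-minute walk is replaced when subjects lose the ability to walk, so that the worst decliners vanish from the analysis. The documents do not support this. They give no trigger for the substitution, do not tie it to loss of ambulation, and do not rule out choosing one test at baseline and keeping it. What is established is that a change of test leaves no valid pair and that no rule covers it.

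Finally, the Jebsen schedule is openly stated and section 7.2.7 plans no head-to-head comparison of endpoints. The 24-month interval is a caution for the endpoint-selection objective, not an error in itself.

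**Conclusion.** The concern holds in limited form. Section 7.2.7 fixes no common timepoint and makes no allowance for length of follow-up, although a third of the subjects (4/12) have already left a study of a progressive disease. On the better-supported reading, mean 30-month decline in the functional tests would be understated by about 7% to 30%. This assumes linear decline at equal rates, eight subjects tested at Day 912, no replacements, and all four leavers last tested between Day 730 and Day 85. If Day 912 was intended, the direction of any bias is unknown.

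That walk-test changes understate decline is possible if those who change worsen faster, but this is not documented. QMA and the primary objectives are not affected. The change is worth making because it is cheap and the results are meant to inform later trials.

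**What to change.** In section 7.2.7:
- Replace the last visit with change from baseline at Days 365, 730 and 912, reporting n at each (Days 365 and 730 only for Jebsen).
- Add a slope over time that uses all visits from every subject, for example a mixed model with time. This lets leavers contribute over their own follow-up and gives short follow-up less weight than a simple per-subject annualised change.
- Where candidate endpoints are compared, use a common 24-month interval.
- Analyse within-subject walk change only where the same test was used at both visits, and report how many subjects changed test or could not perform it.

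In section 5.2.1.4 and Appendix C, reconcile the 10-metre walk with the 10-metre run.

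While the sentence is open, a separate correction is due: the Wilcoxon rank sum test is for independent samples, and paired change calls for the signed-rank test.

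The cost is wording, a few more tables and a little more analysis work on data already scheduled. Later fixed-visit tables will have fewer subjects, and a slope from about 12 subjects will be imprecise, so the two should be read together.
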